Bladder instillation will be performed weekly with the same mixture that the patient was randomized to (mixture with or without Kenalog) and for 6 weeks. Symptom questionnaires will be given at baseline, 3 weeks, and 6 weeks of treatment. If the patient misses a study appointment, she will be called by telephone and queried about side effects and if appropriate, re-scheduled for an appointment.

We plan to recruit patients from January 2019 until July 2020. Patient follow up will be completed by September 2020. As bladder instillations are commonly performed and considered low risk, no interim analysis will be performed. Urinary tract infection will not be considered an adverse event related to study drug but will be monitored in data collection.

Sample size

Sample size calculation was based on the primary outcome, the O'Leary-Sant score on the final day of bladder instillation treatment as compared between the two treatment groups. Based on previous studies, patients have a baseline IC/BPS score following standard medical treatment of approximately 24 ± 5.6 points.[16,17] A 4.03 point decrease from baseline on the O'Leary-Sant questionnaire corresponds with at least a 50% perceived improvement in the patient's disease.[24] We believe this level of difference between the groups in the final O'Leary-Sant scores would be clinically significant. We want 80% power to detect a 4.03 point decrease from a baseline mean score of 24 (expected score in the bladder instillation without Kenalog group after treatment) with a standard deviation ≤ 5.6 points (alpha 0.05) with a 2-sided t-test. The G*Power sample size calculator was used for the power calculations (<https://www.stat.ubc.ca/~rollin/stats/ssize/n2.html>) and these calculations were confirmed for accuracy by a University of Louisville biostatistician. The resulting sample size was $n= 32$ for each group for a total of 64 enrolled patients. Accounting for a 20% dropout in the study, this would translate to a sample size of 80 patients enrolled with a goal of 40 per group.

Recruitment

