All identifying information and data collected during the course of this study will be kept secure and strictly confidential. All data will be stored electronically on a password protected, encrypted laptop in the possession of the study investigator. Risks for breaches of confidentiality will be minimized by entering data from the medical record to a password protected, encrypted computer database which will have limited access to the PI.

The patient's unique study ID will be used for storage, analysis and publication.

Paper data collections forms will be utilized and data will be entered from the paper data form by a study investigator into either a RedCap database or an encrypted, password protected laptop or computer Excel database. These data forms will be housed in a locked file cabinet in the Division of Female Pelvic Medicine and Reconstruction office in a locked cabinet with restricted access.

Data Analysis and Statistical Methods:

The data will be analyzed in consultation with a department-committed biostatistician utilizing SPSS statistical software. Categorical variables (e.g. 'yes" to certain questions on the PFDI) will be compared using chi-square tests (or Fisher's exact test when appropriate). Continuous variables (such as primary outcome) will be compared using t-tests, and changes in continuous outcomes over time (e.g. change from baseline to 8-week O'Leary-Sant score) will be compared with paired t-tests. A regression analysis will be performed to determine the impact of various relevant cofactors (e.g. patient age, presence of other chronic disorders, level of OAB symptoms) on the relationship between group assignment and treatment outcomes.

We will perform an intention-to-treat analysis by the assigned study groups for the initial analysis, comparing women who followed up at the completion of the study (6-week outcomes) between the study groups (bladder instillations with and without Kenalog) as

Study Title: Randomized controlled trial comparing two different bladder instillation treatments for interstitial cystitis/bladder pain syndrome.
assigned. We will also perform a per-protocol analysis, comparing women in the bladder instillation with Kenalog who had at least 4 bladder instillation treatments to the group that had bladder instillations without Kenalog. Lastly, we will perform two types of sensitivity analysis:

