- (1) Imputation of missing data with assumption of treatment non-response (baseline O'Leary-Sant and other outcomes scores carried forward as the final outcome)
- (2) Imputation of missing data with assumption of “best last known” response (final outcomes assumed to be the best value for that outcome during the study course that was available)
- (3) Imputation of missing data with “most recent last known” response (final outcomes assumed to be the most recent value for that outcome during the study course that was available)

Planned secondary analyses will include: (1) treatment response of subgroups of patients with and without prominent OAB symptoms (OABq score ≥ 8); (2) treatment response in patients with and without a history of prior IC/BPS treatment; and (3) the relationship between known coexisting pain and irritative organ disorders (irritable bowel syndrome, fibromyalgia, chronic pain, chronic pelvic pain, vulvodynia, anxiety, depression, chronic fatigue syndrome) and response to treatment; (4) Treatment cost-analysis. The interaction of these factors (prominent OAB symptoms, prior IC/BPS treatment, coexisting pain or irritative organ disorders) with the relationship between randomization and treatment response will be determined.

Potential Benefits:

Participants may benefit from the multiple agents in the bladder instillation, including Kenalog, a steroid. Steroids have been shown to be helpful in patients with IC/BPS. Bladder instillation therapy is a well-tolerated and commonly used treatment of IC/BPS.

Potential Risks:

This research study cannot practically be conducted without access and use of protected health information. Thus, the principle risk to patients involved in the study is a potential breach of confidentiality and misuse or exposure of this information. With this in mind, the investigators will conduct all research activities in such a way that maximizes data security and minimizes any risk of potential data breaches.

Patients may have risk of embarrassment or offense due to the private and personal nature of some of the study questions (e.g. such as questions about urinary incontinence or sexual activity). This risk will be minimized by accurate description of the nature of the study and the study outcomes to the patient prior to informed consent, and communication with the patient regarding the right to decline to answer any given study question.

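### The only checks on dropout are three single-value fills, which can understate or miss bias from women who worsened and left; a tipping-point analysis by arm is needed

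*Combined protocol and SAP*

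**What the plan says.** All of this is in the combined protocol and SAP. Under Data Analysis and Statistical Methods, the initial analysis is called intention-to-treat but is defined as "comparing women who followed up at the completion of the study (6-week outcomes) between the study groups". It is therefore a comparison of completers, as assigned.

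The same section then says "we will perform two types of sensitivity analysis" and lists three:

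1. Non-response assumed: "baseline O'Leary-Sant and other outcomes scores carried forward as the final outcome".
2. Best last known: "final outcomes assumed to be the best value for that outcome during the study course that was available".
3. Most recent last known: "final outcomes assumed to be the most recent value for that outcome during the study course that was available".

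Under Participant timeline, questionnaires are given at baseline, 3 weeks and 6 weeks only. Under Sample size, enrolment is raised from 64 to 80: "Accounting for a 20% dropout in the study". Under Interventions, a woman may stop after a reaction or by choice. No multiple imputation, likelihood-based repeated-measures model, delta adjustment or tipping-point analysis is described. The plan does not say whether baseline counts as an available value in rule (2).

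**The concern.** A completers-only comparison is unbiased only if the women who leave resemble, arm by arm, those who stay. The sensitivity analyses are the only place where the plan tests that assumption. A useful check must be able to represent the troubling case, in which women in one arm leave because their symptoms got worse. Rules (1) and (2) largely cannot represent it, and rule (3) does so only in part.

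There are two further weaknesses. Each rule inserts one value and analyses it as if observed, so the standard error carries no imputation uncertainty. And where both arms improve but dropout is unequal, carrying old scores forward penalises the arm that lost more women, even if they left at random.

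At stake is whether the report can say that its conclusion withstands dropout. With about 8 of 40 women missing per arm, that statement matters.

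**Working it through.** **The plan's own figure.** Inputs from Sample size: difference 4.03, SD 5.6, two-sided alpha 0.05, power 80%. The t-test has power 0.796 with 31 per group and 0.809 with 32, so 32 per group is right. 64/(1 − 0.20) = 80. The sample size reproduces and is not in question.

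**What each rule can return.** A woman without a week-6 score has at most baseline and week 3 (lower is better).

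| Baseline | Week 3 | True week 6 | Rule (1) | Rule (2), baseline counted | Rule (3) |
|---|---|---|---|---|---|
| 24 | 27 | 30 | 24 | 24 | 27 |
| 24 | none | 30 | 24 | 24 | 24 |
| 24 | 20 | 30 | 24 | 20 | 20 |

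If baseline is not counted, week 3 is the only value left and rule (2) equals rule (3).

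**Tipping point at the design values.** Completers 19.97 (Kenalog) v 24.00, 32 per arm; 8 of 40 missing per arm; control dropouts average 24.
- Completers: SE = 5.6 × √(2/32) = 1.40; t = 4.03/1.40 = 2.88; p = 0.005.
- Kenalog dropouts filled at 24: mean 0.8 × 19.97 + 0.2 × 24 = 20.78; difference 3.22. Kenalog variance 5.6² + 0.2 × 0.8 × 4.03² = 33.96; SE = √(33.96/40 + 31.36/40) = 1.278; t = 2.52; p = 0.014.
- Filled at 28: difference 2.42, p = 0.08.
- Significance is lost at 26.9 with the single-imputation SE. With the completers' SE it is lost at 19.97 + (4.03 − 1.999 × 1.40)/0.2 = 26.1.

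So the conclusion changes when these 8 women average about 2 to 3 points worse than baseline. Rules (1) and (2) cannot place any woman above her own baseline. Rule (3) can, but only through a worsened week-3 score.

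**Worsening-related dropout in one arm.** Assumptions, none from the documents: both arms start at 24; 20% of Kenalog women leave 6 points worse and already fully so at week 3; 20% of controls leave at random, half improved (21) at week 3; everyone else improves by 6; every dropout has a week-3 score; correlation 0.5 between visits.
- Truth: Kenalog 0.8 × 18 + 0.2 × 30 = 20.4; control 18; difference +2.4 against Kenalog.
- Completers: 18 − 18 = 0.0.
- Rule (1): 19.2 − 19.2 = 0.0.
- Rule (2): the mean of the better of baseline and week 3 is 23.59 in Kenalog dropouts and 19.95 in control dropouts; 0.2 × (23.59 − 19.95) = +0.7.
- Rule (3): 0.2 × (30 − 21) = +1.8.
- With only half the worsening present at week 3: rule (3) 0.2 × (27 − 21) = +1.2; rule (2) +0.6.

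**Random but unequal dropout, no true effect.** Both arms improve by 6; 30% lost in one arm, 10% in the other; week 3 half improved; correlation 0.5. The difference is against the arm that lost more.
- Rule (1): (24 − 0.7 × 6) − (24 − 0.9 × 6) = 1.2 points; simulated type I error 12 to 14%.
- Rule (3): (0.7 × 18 + 0.3 × 21) − (0.9 × 18 + 0.1 × 21) = 0.6 points; 7 to 8%.
- Completers: 0.0 points; about 5%.

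**Noise credit under rule (2).** A woman with no true change gains 5.6 × √((1 − ρ)/π) = 2.23 points at ρ = 0.5 and 1.73 at ρ = 0.7, from taking the better of two noisy readings. This is per dropout: at 20% dropout it moves an arm mean by 0.2 × 2.23 = 0.45 points and cancels if dropout is equal.

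**Would plain imputation be enough?** In the worsening example, regression imputation by arm from baseline and week 3 has a week-3 slope of 1/3 when all correlations are 0.5. Kenalog dropouts are filled at 18 + 9/3 = 21, so the difference is 0.2 × 3 = +0.6. With a week 3–6 correlation of 0.7 the slope is 0.6, the fill 23.4 and the difference +1.1. Both recover less of the true +2.4 than rule (3).

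**The case against.** A reader might infer that the three checks will agree with a biased completers' result and so falsely certify it. The documents do not support that as a general statement. In the worsening example only rule (1) matches the completers; rules (2) and (3) move away by 0.7 and 1.8 points, and the completers' result is itself null. The unequal-dropout example is a false alarm, not a false confirmation: completers are unbiased and the fills disagree with them. False confirmation does occur in simulation with no true effect, when Kenalog women leave because they worsen and controls leave at random. But all three rules then repeated a falsely significant completers' result in anything from 30% to 91% of runs, depending on when women left and whether both arms improved.

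Nor do the documents predict worsening that differs by arm. Potential Risks and Harms speak of discomfort and allergy, not rising O'Leary-Sant scores, and Retention and follow-up plans calls and rescheduling after missed visits. Rule (1) is an openly stated non-response assumption that departs from completers whenever they improve. The 2.2-point noise credit should not be set against the 4.03-point between-arm target.

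All of that stands and limits the claim. What remains is that rules (1) and (2) cannot enter the region where the conclusion would change, and that the calls described ask about side effects rather than collect a score. The reading of rule (2) is also an inference, though the alternative makes it redundant.

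**Conclusion.** The point holds in limited form. With worsening-related dropout that differs by arm, the planned checks can understate or miss the bias: in the example they show 0.0, +0.7 and +1.8 against a true +2.4. At the design values the conclusion turns when 8 Kenalog dropouts average about 26 to 27, beyond what rules (1) and (2) can represent if those women's baselines average 24. With unequal random dropout and improvement in both arms, the fills can produce a spurious difference against the arm with more dropout.

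The mechanisms, dropout shares by arm and correlations are assumptions, and both size and direction change with them. With equal, uninformative dropout there is no bias. It would go too far to conclude that the result will favour Kenalog or that the checks are bound to agree. This should be changed in the SAP; it does not affect the sample size or the conduct of the trial.

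**What to change.** - Add multiple imputation by arm from baseline and week-3 scores, with a delta adjustment that worsens the imputed week-6 scores separately in each arm until the conclusion changes. Make this the main sensitivity analysis and report the tipping values.
- Drop rule (2).
- Keep rules (1) and (3) only as labelled reference analyses. Do not replace rule (3) with unadjusted imputation, which recovered less of the worsening in the example above.
- Correct the announced count of two so that it matches the final list.

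The cost is SAP wording, a few hours of programming and one more table. No new data or patients are needed, because week-3 scores are already collected and enrolment stays at 80.
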